2. RAP AMENDMENTS

18- Oct-2017: Given the decision to not continue the TRPV4 HF work on this asset, the exploratory Bayesian analysis was removed. Addition of some FDAAA required tables, listing, and figures.

3. SUMMARY OF KEY PROTOCOL INFORMATION

3.1. Changes to the Protocol Defined Statistical Analysis Plan

There were no changes or deviations to the originally planned statistical analysis specified in the protocol amendment 02 (Dated: 19-APR-2016).

3.2. Study Objective(s) and Endpoint(s)

Objectives	Endpoints
Primary Objectives	Primary Endpoints

 To assess the effect of GSK2798745 on pulmonary gas transfer 	
 Change in the diffusing capacity for carbon monoxide (DLco)
Secondary Objectives	Secondary Endpoints

 To assess the effect of GSK2798745 on alveolar-capillary conductance (DM) 	
 Change in the diffusing capacity for nitric oxide (DLno), membrane conductance (DM), and capillary blood volume (Vc)

 To assess the effect of GSK2798745 on pulmonary gas transfer following exercise and following an intravenous saline infusion 	
 Change in diffusing capacity for carbon monoxide (DLco)

 To evaluate the effect of GSK2798745 on ventilatory efficiency 	
 Change in the VE/VCO₂ slope determined during a standardized 3-minute step test

 To evaluate the effect of GSK2798745 on pulmonary function 	
 Changes in spirometry measures including forced vital capacity (FVC) and forced expiratory volume in 1 second (FEV1) as well as forced expiratory flows, FEF25-75 FEF50, and FEF75 Change in functional residual capacity (FRC) and end-expiratory lung volume (EELV) measured by body plethysmograph

 To assess the effect of GSK2798745 on dyspnea 	
 Change in dyspnea score

 To assess the effect of GSK2798745 on respiratory rate 	
 Change in respiratory rate continuously measured by body sensor (Preventice Body Guardian)

 To evaluate the safety and tolerability of repeat administration of GSK2798745 	
 Clinical monitoring of vital signs, ECGs, and clinical laboratory safety data, including LFTs and troponin as well as reporting of adverse events (AEs)

 To assess the effect of GSK2798745 on quality of life 	
 Change in SF-36 acute score

 To characterize the pharmacokinetic profile of GSK2798745 in subjects with heart failure 	
 Area under the concentration time curve (AUC), maximum drug concentration (Cmax), time to maximum observed plasma concentration (tmax), and elimination halflife (T½)

Objectives	Endpoints
Exploratory Objectives	Exploratory Endpoints

 To determine the effect of GSK2798745 on oxygen saturation To assess effect of GSK2798745 on sleep disordered breathing patterns 	
 Change in minimum O₂ saturation measured during polysomnography Change in apnea-hypopnea index (AHI) determined by polysomnography Change in the central, obstructive and mixed apnea indexes as determined by polysomnography Change in respiratory temporal dynamics during in-house sleep apnea evaluation

 To determine whether GSK2798745 affects sleep-disordered breathing leading to an improvement in sympathoadrenal activity To determine whether GSK2798745 affects electrocardiographic parameters 	
 Change in plasma and urinary catecholamine concentrations in subjects with sleep-disordered breathing Changes in time and frequency domain analyses of ECG: HR variability to define sympathetic activity

 To explore the impact of GSK2798745 on the exposure of HMG-CoA reductase inhibitors and their key metabolites 	
 AUC of HMG-CoA reductase inhibitors and their key metabolites

3.3. Study Design

Overview of Study Design and Key Features	

Period I
 
Period II
 
Screening → GSK2798745 7 days or Placebo 7 days → 14-day Washout → GSK2798745 7 days or Placebo 7 days → Follow-up
 
Legend:
 
 Sleep Study (Optional) DLco (PFTs) Exercise DLco* Saliva Infusion* 
*Eligible Subjects Only
	
Design Features	
 This is a randomized, double-blind, sponsor-unblinded, placebo-controlled, 2 X 2 crossover study in adults with heart failure. The

Overview of Study Design and Key Features	
	
study will be conducted at multiple centers.
 
 Subjects have an at least 3 month history of HF, be a NYHA Class II-IV, a NT-proBNP of greater than 400 pg/ml within the last 6 months and a % predicted DLco of < 80% at screening.
Dosing	
 Subjects are dosed once daily for 7 days. Then there is a wash out period of at least 14 days, followed by another 7 days of once daily dosing.
Treatment Assignment	
 Eligible subjects will be randomized to one of two treatment sequences. A sufficient number of subjects with heart failure will be enrolled so that 12 subjects complete the two study periods and critical assessments. Subjects will receive either GSK2798745 or placebo once daily for a period of 7 days. After at least a 14-day washout period (preferably not greater than 30 days from last dose in Period I), subjects will participate in a second, identical 7-day study period and receive the alternate study medication.
Interim Analysis	
 After approximately 5-6 subjects complete both study periods, a sponsor unblinded interim analysis will be performed. After approximately 9 subjects complete both study periods, a sponsor unblinded interim analysis will be performed. After 12 subjects complete both study periods, prior to SAC, an interim analysis will be performed to determine if additional subjects will be enrolled in the study (up to 24 subjects). Full details are in Section 3.1

3.4. Statistical Hypotheses

An estimation approach will be used for the comparison between GSK2798745 treatment and placebo for the change from baseline in DLCo at day 4 and day 7. Point estimates and associated 95% confidence intervals for the differences in means will be constructed to provide a plausible range of values for the true comparisons of interest.

4. PLANNED ANALYSES

4.1. Interim Analyses

- There will be ongoing data reviews by the study team of the un-blinded safety and pharmacokinetics data throughout the trial progression.
- After approximately 6 Subjects complete both study periods, a sponsor un-blinded interim analysis will be performed on DLco and other variables of potential clinical relevance. The programming code for this interim analysis will be provided by the study statistician.

- After approximately 9 subjects complete both study periods, a sponsor un-blinded interim analysis will be performed.
- After 12 subjects complete both study periods, prior to DBF, a sponsor un-blinded interim analysis will be performed on DLco.

A Bayesian predictive probability of change in DLco with 18 patients will be calculated, and the intra-subject variability will be estimated. These analyses will inform a decision to enrol up to 12 additional subjects.

Given the decision to not continue the TRPV4 HF work on this asset, the Bayesian prediction was performed on 10 subjects and a decision was made to only enrol one more patient. Therefore, an interim analysis will not be performed on 12 subjects.

4.2. Final Analyses

The final planned analyses will be performed after the completion of the following sequential steps:

1. All subjects have completed the study as defined in the protocol.
2. All required database cleaning activities have completed the final database release and database freeze has been declared by Data Management.
3. All criteria for unblinding the randomisation codes have been met.
4. Randomisation codes have been distributed accordingly to RandAll NG procedures.

5. ANALYSIS POPULATIONS

Population	Definition / Criteria	Analyses Evaluated
All Subjects	
 The 'All Subjects' Population is defined as all randomized subjects who receive at least one dose of study medication. 	
 • Study Population • Safety/tolerability •
Enrolled	All participants who sign informed consent and for whom a record exists on the study database. This population will be used for the tables/listings of reasons for withdrawal before randomization and listings of AEs and SAEs for non-randomized participants.	
 • Subject Disposition • Reasons for withdrawal before randomization. • Inclusion, exclusion, and randomization criteria deviations
Analysis Population	
 Subjects in the 'All Subjects' population having baseline and post-baseline assessments of the endpoint of interest for both periods 	
 • Efficacy • PD/Biomarker
Screening Population	
 The "Screening Population" is defined as all subjects who were screened as potential patients for the trial 	
 • Screen Failure
Per Protocol	
 Any 'Analysis Population' subjects who are compliant with protocol-specific criteria. Subjects with specified protocol deviations will be excluded. 	
 • Efficacy
PK Population	
 This population will include all subjects in the Safety Population for whom a pharmacokinetic blood sample was obtained and assayed. 	
 • Concentration data summaries,

Population	Definition / Criteria	Analyses Evaluated
		listings, and graphs (including concentration-time profiles as appropriate)
PK Parameter Population	
 This population will include all subjects in the PK Concentration Population for whom valid and evaluable pharmacokinetic parameters were derived. 	
 Listings, summary and analyses of PK parameters

NOTE :

- Please refer to Section [11.13 Appendix 11: List of Data Displays](#) which details the population to be used for each display being generated.

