5.5.3. Other Dose Adjustment/Stopping Safety Criteria

For an individual study participant, additional stopping criteria include, but are not limited to:

- Significant changes to medication (e.g., diuretics) as judged by the Principal Investigator in consultation with the Medical Monitor if necessary
- An emergency room (ER) visit or hospitalization for treatment of an episode of acute decompensated heart failure (ADHF)
- Severe signs or symptoms or significant changes in any of the safety assessments (e.g., ECG, vital signs, laboratory tests) that put the safety of the individual at risk, as judged by the Principal Investigator in consultation with the Medical Monitor if necessary.

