9.3. Data Analysis Considerations

9.3.1. Analysis Populations

All Subjects Population

The ‘All Subjects Population’ is defined as all randomized subjects who receive at least one dose of study medication.

Per Protocol Population

The ‘Per Protocol Population’ will consist of any Analysis Population subjects who are compliant with protocol-specific criteria. Subjects with specified protocol deviations will be excluded.

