9.4. Key Elements of Analysis Plan

Final analysis will be provided when all subjects have finished the study and the database has been frozen. The construction of analysis data sets will be performed in accordance with all applicable GlaxoSmithKline standards and procedures.

Adjustment for multiplicity of treatment group comparisons and endpoints is not planned. All available data will be used in the analyses as defined in the populations above. Missing values will not be imputed.

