8. PRIMARY STATISTICAL ANALYSES

8.1. Efficacy Analyses

8.1.1. Overview of Planned Efficacy Analyses

The efficacy analyses will be based on the “Analysis Population”, unless otherwise specified.

Table 3 provides an overview of the planned efficacy analyses with full details of data displays being presented in [Appendix 11: List of Data Displays](#).

Table 3 Overview of Planned Efficacy Analyses

ENDPOINT	Absolute						Change from Baseline							
	Stats Analysis			Summary		Individual		Stats Analysis			Summary		Individual	
	T	F	L	T	F	F	L	T	F	L	T	F	F	L
DLco														
Diffusing capacity for carbon monoxide (DLco)	Y			Y	Y		Y	Y			Y	Y		Y

NOTES :

- T = Table, F = Figure, L = Listing, Y = Yes display generated.
- Stats Analysis = Represents TFL related to any formal statistical analyses (i.e. modelling) conducted.
- Summary = Represents TFL related to any summaries (i.e. descriptive statistics) of the observed raw data.
- Individual = Represents FL related to any displays of individual subject observed raw data.

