11.6. Appendix 6: Premature Withdrawals & Handling of Missing Data

11.6.1. Premature Withdrawals

Element	Reporting Detail
General	
 Subject study completion was defined as Safety who either prematurely withdrawn or completed FU visits and assessments. Withdrawn subjects were not replaced in the study. All available data from subjects who were withdrawn from the study will be listed and all available planned data will be included in summary tables and figures, unless otherwise specified.

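### The SAP's both-periods rule for the Analysis Population drops usable DLco data from subjects who leave early, and that exclusion can be related to outcome

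*SAP*

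**What the plan says.** **SAP.** Section 5 admits to the Analysis Population only subjects "having baseline and post-baseline assessments of the endpoint of interest for both periods". Section 8.1.1 opens "The efficacy analyses will be based on the" and names this population; Section 9.1.1 does the same for secondary efficacy, and Table 2.04 runs the DLco model on it. Respiratory rate (Table 2.20) and troponin (Tables 2.18 and 2.19) use All Subjects instead, as do the efficacy listings. Section 11.6.1 states that for withdrawn subjects "all available planned data will be included in summary tables and figures", unless otherwise specified, and that withdrawn subjects were not replaced. Section 3.1 declares no change from protocol amendment 02.

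**Protocol.** Section 9.3.1 defines two populations. All Subjects "is defined as all randomized subjects who receive at least one dose of study medication". Per Protocol "will consist of any Analysis Population subjects who are compliant with protocol-specific criteria", but the section does not say what the Analysis Population is. Section 9.4 adds: "All available data will be used in the analyses as defined in the populations above. Missing values will not be imputed".

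**Model.** Protocol 9.4.1 and the SAP synopsis both plan a repeated-measures mixed model for change from baseline in DLco, with a random subject effect. SAP 8.1.2 calls it a repeated-measures ANOVA and does not restate the random effect.

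**Leaving the study.** Under Protocol 5.5, withdrawal from treatment is withdrawal from the study. The individual stopping criteria in 5.5.3 include significant medication changes, with diuretics as the example, and "An emergency room (ER) visit or hospitalization for treatment of an episode of acute decompensated heart failure (ADHF".

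**The concern.** A model with a random subject effect does not need both periods from every subject. The both-periods rule still removes two kinds of valid DLco data: on-treatment values from a subject who leaves in Period I once Day 4 has been measured, and a full Period I from a subject who leaves Period II before any post-baseline value.

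If departures were unrelated to DLco, the only cost would be some precision. The listed triggers, however, are signs of worsening heart failure, and the drug is meant to reduce lung fluid. Subjects who do badly in Period I are then the likeliest to be missing, which can distort the treatment difference. The rule also works endpoint by endpoint. Under Protocol Appendix 9, a subject who meets the infusion stopping criteria in Period I should not have a second infusion, and so drops out of the post-saline DLco summaries without leaving the study (although the Period I post-infusion value may be missing anyway).

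**Working it through.** **1. The plan's own figures.** Inputs from Protocol 9.2 and 9.2.2: N = 12, effect 2.3, SDw 1.5 (also 1.9 and 2.4), two-sided alpha 0.05. SE = SDw × √(2/N), with N − 2 = 10 df.
- SDw 1.5: SE = 1.5 × √(2/12) = 0.612; half-width = 2.228 × 0.612 = 1.364 (stated 1.36); power from the noncentral t is 92.2% (stated above 90%).
- SDw 1.9: half-width 1.728, power 76.2% (stated 1.73, 76%).
- SDw 2.4: half-width 2.183, power 56.3% (stated 2.2, 56%).

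The figures reproduce, and they assume 12 subjects with both periods. At SDw 1.5, 11 such subjects give half-width 1.45 and power 89%; 10 give 1.55 and 85%; 9 give 1.67 and 80%.

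**2. Precision lost.** Let c be the between-period correlation of a subject's changes, c = sb²/(sb² + SDw²), where sb is the between-subject SD of the change. The documents do not give sb; I assume 0.75 to 3.0. A one-period subject carries (1 − c)/2 of the information of a two-period subject. At SDw 1.5:
- sb 0.75: c = 0.5625/2.8125 = 0.2, so 40%
- sb 1.5: c = 0.5, so 25%
- sb 3.0: c = 9/11.25 = 0.8, so 10%

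Example: ten two-period subjects plus one one-period subject per sequence. Both-periods SE = 1.5 × √(2/10) = 0.671. All-data SE = 0.671/√(1 + 2 × 0.40/10) = 0.645 at sb 0.75, and 0.664 at sb 3.0. Generalised least squares with intercept, period, treatment and random subject gives the same values, and for 12 dosed subjects:

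| One-period subjects | SE, both-periods set | SE, all data | Reduction |
|---|---|---|---|
| 1 | 0.642 | 0.630 to 0.639 | 0.5% to 1.9% |
| 2 | 0.671 | 0.645 to 0.664 | 1.0% to 3.9% |
| 3 | 0.712 | 0.666 to 0.699 | 1.8% to 6.5% |

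**3. Bias.** Assumptions: SDw 1.5, sb 0.75 to 1.5, one change value per period, and departure after Period I when the observed change falls below a cut-off. Large-sample simulation, 400,000 subjects per sequence:

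| True effect | Who leaves | Both-periods estimate | Bias |
|---|---|---|---|
| 2.3 | below −1.5, either treatment, all leave | 2.10 to 2.12 | −0.20 to −0.18 |
| 2.3 | same, half leave | 2.21 to 2.23 | −0.09 to −0.07 |
| 0 | below −1.5, either treatment | 0.00 | 0 |
| 0 | below −1.0, active only | 0.28 to 0.31 | +0.28 to +0.31 |
| 0 | below −1.0, placebo only | −0.31 to −0.28 | −0.31 to −0.28 |
| −1.0 | below −1.5, either treatment, all leave | −0.87 to −0.80 | +0.13 to +0.20 |

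The all-data mixed model recovered the true effect, to within 0.01, in every row.

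Hand check of the fourth row at sb 0.75: SD of the change = √2.8125 = 1.677 and z = −1.0/1.677 = −0.596. Those who stay have mean Period I change 1.677 × 0.334/0.7245 = 0.773. A fraction c = 0.2 of that persists into Period II, so their within-subject difference is shifted by 0.8 × 0.773 = 0.618. The other sequence is unaffected, so the estimate shifts by 0.618/2 = 0.31.

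One extreme case goes further: true effect −1.0 with departure below −1.0 on active only gives −0.58 to −0.47, a bias of +0.42 to +0.53. It needs half of the active-first sequence to leave.

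**The case against.** Several stronger readings are tempting, and the documents do not support them.

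- **That the SAP contradicts the protocol.** A reader might infer this from the all-available-data sentence in Protocol 9.4. That sentence is tied to the populations defined before it, and the protocol itself uses the term Analysis Population. The SAP fills a gap; the fault is that it does so while declaring no change. Likewise, SAP 11.6.1 yields to anything specified elsewhere, and it covers displays rather than the model.
- **That every efficacy analysis is affected.** Respiratory rate and troponin are not, and the listings keep the excluded subjects visible.
- **That only subjects who complete both periods are kept.** One post-baseline value per period is enough, so a subject who leaves in Period II after Day 4 stays in. This matters for size. Take SDw 1.9 on each raw reading, a true effect of 2.3, and departure when the Day 4 change is below −3. The SD of the change is 1.9 × √2 = 2.69, so the chance of leaving is 0.132 on placebo and 0.024 on active. Expected exclusions are 12 × (0.132 + 0.024)/2 = 0.94. Wrongly counting Period II departures as well would give 12 × (1 − 0.868 × 0.976), about 1.8.

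The remaining objections have force. Protocol 4.4 expects subjects to complete, no dropout rate is given, and no document ties withdrawal to a DLco cut-off, so every bias figure is a scenario. The clean result for the all-data model is partly built in, because departure was made to depend only on observed values. A subject who leaves before any post-baseline DLco adds nothing under either population. Restricting the DLco model to one of the two sites (SAP Table 2.04) probably costs more subjects than this rule. The secondary gas-transfer models in SAP Table 4 are on absolute values, where c is likely higher and one-period subjects add less. In an estimation-only Phase 2a crossover, a set in which each subject supplies a within-subject contrast is a defensible choice.

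**Conclusion.** The point holds as a modest one. The SAP adds a both-periods condition that no population defined in the current protocol contains, applies it to the primary DLco model, and records no change. It discards data that the planned model can use, and Protocol 5.5 and 5.5.3 make it plausible that the discarded subjects differ in outcome.

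On the assumptions above, the bias is about 0 to 0.3 mL/mmHg/min in either direction, up to 0.31/2.3 = 13% of the planned effect. It exceeds that only in the extreme harmful-effect case. It vanishes with no true effect and the same withdrawal rule on both treatments, so it needs either a real effect or treatment-related withdrawal. The precision at stake is small. Whether any subject is affected cannot be told from the documents. What gives the point some weight is that losses are hard to absorb. Protocol 9.2.1 allows replacement, but SAP 11.6.1 says there was none, and SAP 4.1 reports a decision to enrol only one more patient after a prediction made on 10.

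**What to change.** - Fit the primary DLco mixed model, and any secondary gas-transfer endpoint that is modelled, on all dosed subjects with a baseline and at least one post-baseline value in any period. State the random subject effect in SAP 8.1.2, since one-period subjects contribute only if it is kept.
- Keep the both-periods set as a sensitivity analysis and report the two results together.
- Record the population definition, and its departure from the protocol, in SAP 3.1. Because the sponsor is unblinded and interim looks have taken place, date the entry.
- Align the figure shells in SAP Appendix 12, headed All Subjects, with the display list in Appendix 11, which mostly gives Analysis.

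The cost is SAP wording and one extra model run, with no new data. The downside is that the all-data result relies on a missing-at-random assumption: departure may depend on observed DLco but not on unobserved values. The sensitivity analysis shows how far the estimate moves between the two sets; it does not test that assumption.

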5.1. Protocol Deviations

- Important protocol deviations (including deviations related to study inclusion/exclusion criteria, conduct of the trial, patient management or patient assessment) will be summarised and listed.
- Important deviations which result in exclusion from the analysis population will also be summarised and listed. (Please refer to [Appendix 1: Protocol Deviation Definitions for Per Protocol Population](#)).
- Protocol deviations will be tracked by the study team throughout the conduct of the study in accordance with the Protocol Deviation Management Plan.
 - Data will be reviewed prior to unblinding and freezing the database to ensure all important deviations and deviations which may lead to exclusion from the analysis are captured and categorised on the protocol deviations dataset.
 - This dataset will be the basis for the summaries and listings of protocol deviations.

6. GENERAL CONSIDERATIONS FOR DATA ANALYSES AND DATA HANDLING CONVENTIONS

- There are no planned examinations of covariates. The only subgroups analysis planned is by site.
- There are no planned adjustments for multiple comparisons or multiplicity.

[Table 1](#) provides an overview of appendices within the RAP for outlining general considerations for data analyses and data handling conventions.

Table 1 Overview of Appendices

Section	Component
11.1	Appendix 1: Protocol Deviation Definitions for Per Protocol Population
11.2	Appendix 2: Time and Events

Section	Component
11.3	Appendix 3: Treatment States and Phases
11.4	Appendix 4: Data Display Standards & Handling Conventions
11.5	Appendix 5: Derived and Transformed Data
11.6	Appendix 6: Premature Withdrawals & Handling of Missing Data
11.7	Appendix 7: Values of Potential Clinical Importance
11.8	Appendix 8: Laboratory A&R (QUEST: LAB) Dataset Details
11.9	Appendix 9: Biomarker A&R Dataset Details

